#### **7.1.9 Non-compliance (NIH Definition)**

The failure to comply with applicable NIH Human Research Protections Program (HRPP) policies, IRB requirements, or regulatory requirements for the protection of human research subjects.

#### **7.1.10 Unanticipated Problem**

Any incident, experience, or outcome that:

- Is unexpected in terms of nature, severity, or frequency in relation to
  - (a) the research risks that are described in the IRB-approved research protocol and informed consent document; Investigator's Brochure or other study documents, and
  - (b) the characteristics of the subject population being studied; **AND**
- Is related or possibly related to participation in the research; **AND**
- Suggests that the research places subjects or others at a *greater risk of harm* (including physical, psychological, economic, or social harm) than was previously known or recognized.

### **7.2 NCI-IRB AND CLINICAL DIRECTOR REPORTING**

#### **7.2.1 NCI-IRB and NCI CD Expedited Reporting of Unanticipated Problems and Deaths**

The Protocol PI will report in the NIH Problem Form to the NCI-IRB and NCI Clinical Director:

- All deaths, except deaths due to progressive disease
- All Protocol Deviations
- All Unanticipated Problems
- All non-compliance

Reports must be received within 7 days of PI awareness via iRIS.

#### **7.2.2 NCI-IRB Requirements for PI Reporting Continuing Review**

The protocol PI will report to the NCI-IRB:

1. A summary of all protocol deviations in a tabular format to include the date the deviation occurred, a brief description of the deviation and any corrective action.
2. A summary of any instances of non-compliance
3. A tabular summary of the following adverse events:
  - All Grade 2 **unexpected** events that are possibly, probably or definitely related to the research;
  - All Grade 3 and 4 events that are possibly, probably or definitely related to the research;
  - All Grade 5 events regardless of attribution;
  - All Serious Events regardless of attribution.

**NOTE:** Grade 1 events are not required to be reported.

### **7.2.3 NCI-IRB Reporting of IND Safety Reports**

Only IND Safety Reports that meet the definition of an unanticipated problem will need to be reported to the NCI IRB.

## **7.3 IND SPONSOR REPORTING CRITERIA**

### **7.3.1 Expedited Adverse Event Reporting Criteria to the IND Sponsor**

During the first 30 days after the subject receives investigational agent/intervention, the investigator must immediately report to the sponsor, using the mandatory MedWatch form 3500a or equivalent, any serious adverse event, whether or not considered drug related, including those listed in the protocol or investigator brochure and must include an assessment of whether there is a reasonable possibility that the drug caused the event. For serious adverse events that occur more than 30 days after the last administration of investigational agent/intervention, only report those that have an attribution of at least possibly related to the agent/intervention.

Required timing for reporting per the above guideline:

- Deaths (except death due to progressive disease) must be reported via email within 24 hours. A complete report must be submitted within one business day.
- Other serious adverse events as well as deaths due to progressive disease must be reported within one business day

Events will be submitted to the Center for Cancer Research (CCR) at: [[contact]](mailto:[contact]) and to the CCR PI and study coordinator.

### **7.3.2 Reporting Pregnancy**

#### **7.3.2.1 Maternal exposure**

If a patient becomes pregnant during the course of the study, the study treatment should be discontinued immediately and the pregnancy reported to the Sponsor. The potential risk of exposure of the fetus to the investigational agent(s) or chemotherapy agents (s) should be documented in box B5 of the MedWatch form “Describe Event or Problem”.

Pregnancy itself is not regarded as an SAE. However, as patients who become pregnant on study risk intrauterine exposure of the fetus to agents which may be teratogenic, the CCR is requesting that pregnancy should be reported in an expedited manner as **Grade 3 “Pregnancy, puerperium and perinatal conditions - Other (pregnancy)”** under the *Pregnancy, puerperium and perinatal conditions* SOC.

Congenital abnormalities or birth defects and spontaneous miscarriages should be reported and handled as SAEs. Elective abortions without complications should not be handled as AEs. The outcome of all pregnancies (spontaneous miscarriage, elective termination, ectopic pregnancy, normal birth, or congenital abnormality) should be followed up and documented.

If any pregnancy occurs in the course of the study, then the investigator should inform the Sponsor within 1 day, i.e., immediately, but **no later than 24 hours** of when he or she becomes aware of it.

The designated Sponsor representative will work with the investigator to ensure that all relevant information is provided to the Sponsor within 1 to 5 calendar days for SAEs and within 30 days for all other pregnancies.

The same timelines apply when outcome information is available.

#### **7.3.2.2 Paternal exposure**

Male patients should refrain from fathering a child or donating sperm during the study and for 60 days after the last dose of Mithramycin.

Pregnancy of the patient’s partner is not considered to be an AE. However, the outcome of all pregnancies (spontaneous miscarriage, elective termination, ectopic pregnancy, normal birth, or congenital abnormality) occurring from the date of the first dose until 60 after the last dose should, if possible, be followed up and documented.

### **7.4 DATA AND SAFETY MONITORING PLAN**

#### **7.4.1 Principal Investigator/Research Team**

The clinical research team will meet regularly when patients are being actively treated on the trial to discuss each patient in detail.

All data will be collected in a timely manner and reviewed by the principal investigator or a clinical associate investigator in a timely manner. Adverse events will be reported as required above. Any safety concerns, new information that might affect either the ethical and or scientific conduct of the trial, or protocol deviations will be immediately reported to the IRB using iRIS.

The principal investigator will review adverse event and response data on each patient to ensure safety and data accuracy. The principal investigator will personally conduct or supervise the investigation and provide appropriate delegation of responsibilities to other members of the research staff.

#### **7.4.2 Sponsor Monitoring Plan**

As a sponsor for clinical trials, FDA regulations require the CCR to maintain a monitoring program. The CCR’s program allows for confirmation of: study data, specifically data that could affect the interpretation of primary study endpoints; adherence to the protocol, regulations, and

SOPs; and human subjects protection. This is done through independent verification of study data with source documentation focusing on:

- Informed consent process
- Eligibility confirmation
- Drug administration and accountability
- Adverse events monitoring
- Response assessment.

The monitoring program also extends to multi-site research when the CCR is the coordinating center.

This trial will be monitored by personnel employed by an CCR contractor. Monitors are qualified by training and experience to monitor the progress of clinical trials. Personnel monitoring this study will not be affiliated in any way with the trial conduct.

## **8 STATISTICAL CONSIDERATIONS**

Prior to amendment F, the protocol enrolled 12 evaluable patients, and there were no clinical responses, but dose-limiting hepatotoxicity associated with ABCB4 and ABCB11 genotypes was identified. Thus, the results from these initial 12 patients will be reported as a separate group, and accrual will begin again using the same phase II design as initially proposed, but restricted to patients with favorable SNPs, and receiving the modified dose regimen described in amendment F. Thus, beginning with amendment F, the primary endpoint of this study will be objective response by RECIST criteria v 1.1. Patients will be analyzed in two cohorts (primary thoracic malignancy; extra-thoracic malignancy metastatic to the chest). The best response to mithramycin will be examined for each cohort. In each cohort, the trial will seek to rule out an unacceptably low 5% objective response rate (ORR;  $p_0=0.05$ ), in favor of a higher response rate of 30% ( $p_1=0.30$ ). With  $\alpha=0.10$  (probability of accepting a poor treatment=0.10) and  $\beta = 0.10$  (probability of rejecting a good treatment=0.10), the study will initially enroll 7 evaluable patients in each stratum, and if 0 of the 7 have a response, then no further patients will be accrued in that cohort. If 1 or more the first 7 in a cohort have a response, then accrual would continue until a total of 21 evaluable patients have enrolled in that cohort. As it may take several weeks to determine if a patient has experienced a response, a temporary pause in the accrual to the trial may be necessary to ensure that enrollment to the second stage is warranted. If there are 1 to 2 responses in 21 patients, this would be an uninterestingly low response rate, while if there were 3 or more responses in 21 patients, then this would be sufficiently interesting to warrant further study of the patients from that cohort in later trials. Under the null hypothesis (5% response rate), the probability of early termination in each cohort is 70%.

With two cohorts, up to 42 evaluable patients may be required to be accrued, in addition to the 12 enrolled prior to amendment F. It is expected that 10-15 patients per year may enroll onto this study. Thus, 3-4 years additional may be needed to enroll 42 additional evaluable patients. To allow for a small number of inevaluable patients, and to account for the 12 enrolled prior to amendment F, the accrual ceiling will be set at 57.

The following table summarizes the two stage design that will be used for each cohort in the trial beginning with Amendment F.

---

	Cumulative Number of Responses	Decision
Stage 1: Enter 7 patients	0	Terminate the trial for that cohort: agent ineffective
	1 or more	Inconclusive result, continue trial (proceed to Stage 2)
Stage 2: Enter 14 additional patients	2 or less	Terminate the trial for that cohort: agent ineffective
	3 or more	Terminate the trial: agent effective

---

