#### **1.3.4 Recent Experience with Mithramycin in Adult Oncology Patients at the NCI**

Twelve patients (10 males; 2 females; median age 51y; range 40-72y) with refractory thoracic malignancies (six MPMs, 2 esophageal cancers, two lung cancers, 2 synovial sarcomas) received 6h mithramycin infusions q day x 7, every 28 days. Response rates following two cycles, pharmacokinetics, and systemic toxicities (cycle 1) were evaluated. A total of 20 cycles were administered to 12 patients; all were evaluable for toxicities. No objective responses were observed in 7 patients who were evaluable for treatment responses. No myelosuppression, uncontrollable nausea or vomiting was observed. No patients experienced bleeding. The lack of these toxicities, which have been associated with mithramycin treatment  may be attributable at least in part to higher purity of the current drug relative to what had been used previously.

Eight patients experienced transient, asymptomatic dose-limiting transaminitis following 25mcg/kg/infusions. This toxicity always occurred on day 4 of the infusion. Percutaneous biopsies from three individuals revealed apoptotic hepatocellular death (**Figure 6A**). Four patients (two with MPM) had no hepatotoxicity and tolerated dose escalation to 30 mcg/kg/infusion. Peak and steady state mithramycin levels were 20 and 8nM, respectively, which were not different in patients with or without hepatotoxicity (**Figure 6B**). DMET genotyping revealed that two SNPs (rs2302387 and rs4668115) in genes encoding two related bile transporters (ABCB4 and ABCB11, respectively) were significantly associated with LFT elevations in the 12 patients treated with mithramycin (**Figure 7A** and **Figure 7B**).

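### The accrual ceiling of 57 allows only 3 inevaluable patients among 45 new registrations, with no stated basis and against 5 of the trial's first 12, so 42 evaluable patients and 90% power are not assured if both cohorts reach stage 2

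*Combined protocol and SAP*

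**What the plan says.** Section 8 sets a Simon two-stage design in each of two cohorts. It aims to rule out an "unacceptably low 5% objective response rate" against 30%, with alpha 0.10 ("probability of accepting a poor treatment=0.10") and beta 0.10 ("probability of rejecting a good treatment=0.10"). Stage 1 takes 7 evaluable patients: "if 0 of the 7 have a response, then no further patients will be accrued in that cohort". Otherwise the cohort goes on to 21 evaluable, and 3 or more responses count as success.

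Two cohorts therefore need at most 42 evaluable patients, expected to take 3 to 4 more years at 10 to 15 enrolments a year. The ceiling allows for a small, unquantified number of inevaluable patients and must also "account for the 12 enrolled prior to amendment F, the accrual ceiling will be set at 57".

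Two other places bear on the allowance:

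- **Section 1.3.4** describes the first 12 patients: "Response rates following two cycles, pharmacokinetics, and systemic toxicities (cycle 1) were evaluated". All 12 were evaluable for toxicities, but "No objective responses were observed in 7 patients who were evaluable for treatment responses". Section 8 refers to the same patients as 12 evaluable patients, without saying evaluable for what.
- **Section 8.2** ties evaluability for response to a full course, given there as 4 cycles and 28 doses. Section 3.2 defines a course as three cycles. Section 8.2 also makes patients who progress without completing a full course evaluable for toxicity only.

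**The concern.** The size and power in Section 8 are stated in evaluable patients, but the ceiling counts registrations. The link between the two is the inevaluable rate. The plan never states that rate, and the ceiling implies 6.7%. The only evaluability data in the document point to a much higher figure.

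If more than about 7% of new patients are inevaluable and both cohorts continue, accrual is expected to end before each cohort has 21 evaluable patients. The plan has no rule for declaring a cohort that ends short. The stated power and duration would then describe a trial larger than the ceiling permits.

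**Working it through.** **Inputs.** From Section 8: p0 = 0.05, p1 = 0.30, 7 then 21 evaluable per cohort, stop at 0 of 7, success at 3 or more, ceiling 57, 12 already enrolled. From Section 1.3.4: 7 of 12 evaluable for response. Assumptions: the inevaluable rate d in the new cohorts, shown over a range, and inevaluability independent between patients.

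**1. The plan's design reproduces.** P(success) is the sum over x1 from 1 to 7 of P(X1 = x1) × P(X2 ≥ 3 − x1), with X1 ~ Bin(7, p) and X2 ~ Bin(14, p).

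- Type I error at p = 0.05: 0.064, within the 0.10 limit.
- Power at p = 0.30: 0.904.
- Early termination at p = 0.05: 0.95^7 = 0.698, the stated 70%.

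**2. The allowance.** 57 − 12 = 45 new registrations; 45 − 42 = 3; 3/45 = 6.7%.

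**3. The trial's own experience.** 12 − 7 = 5 not evaluable for response; 5/12 = 42%, exact 95% CI 15% to 72%. If the true rate were 6.7%, the chance of 5 or more in 12 would be 0.0007.

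**4. When all 42 are needed.** Both cohorts must pass stage 1. If both truly respond at 30%, this has probability (1 − 0.7^7)² = 0.84. If both are at 5%, it is (1 − 0.95^7)² = 0.09.

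**5. Yield from 45 registrations when both cohorts continue.** P(at least 42 evaluable) = P(Bin(45, 1 − d) ≥ 42). Expected yield is 45(1 − d). Registrations needed for an expected 42 are 42/(1 − d), rounded up.

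| d | P(≥ 42 evaluable) | Expected evaluable | Registrations for 42 |
|---|---|---|---|
| 6.7% | 0.65 | 42 | 45 |
| 10% | 0.33 | 40.5 | 47 |
| 15% | 0.08 | 38 | 50 |
| 20% | 0.01 | 36 | 53 |
| 30% | 0.0001 | 31.5 | 60 |
| 42% (5/12) | about 0 | 26 | 72 |

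**6. Power and type I error at the size reached.** Same formula as step 1, keeping 0 of 7 and 3 or more responses, with the expected yield split equally between the cohorts.

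| Evaluable per cohort | Approximate d | Power at 30% | Type I error at 5% |
|---|---|---|---|
| 21 | up to 6.7% | 0.904 | 0.064 |
| 19 | 15% | 0.892 | 0.053 |
| 16 | 30% | 0.856 | 0.037 |
| 13 | 42% | 0.776 | 0.023 |

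A simulation of two alternating cohorts under the 45-registration cap, both truly at 30%, agrees: per-cohort power is about 0.90 at d = 10%, 0.88 at 20%, 0.845 at 30% and 0.77 at 5/12.

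**7. Duration at 10 to 15 registrations a year.** 42 registrations take 42/15 = 2.8 to 42/10 = 4.2 years, matching the plan's 3 to 4. 50 take 3.3 to 5.0 years, and 72 take 4.8 to 7.2 years.

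**The case against.** The strongest reply is that 42% should not be carried forward.

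- **Different patients and regimen.** The first 12 were not selected by genotype, and eight had dose-limiting transaminitis. The amended trial admits only favourable genotypes in order to avoid that toxicity. The documents do not say why five patients were inevaluable, and five of 12 is a small sample.
- **Section 8's own wording.** It calls all 12 evaluable. Read literally, that is 0 of 12 inevaluable (exact 95% CI 0% to 26%), which is compatible with 6.7%.
- **42 is a maximum.** It is needed only if both cohorts continue. If one cohort is truly at 30% and the other at 5%, the simulated power of the active cohort is still 0.85 at 5/12 inevaluable.

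Most of this stands, so 42% marks one end of a range and is not a forecast. It does not rescue 6.7%. Section 1.3.4 distinguishes evaluable for toxicity (12) from evaluable for response (7), and response is the primary endpoint. Some features could also raise the rate. The first group was assessed after two cycles, whereas evaluability now requires a full course of three or four. Early progressors are excluded from the response analysis. Later cycles are planned at a higher dose.

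Three stronger inferences are tempting, and the documents support none of them:

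- **That 42 evaluable patients and 90% power will not be delivered.** This depends on both cohorts continuing and on an unknown rate. At 6.7% the chance of reaching 42 is 65%, and at 10% power is still about 0.90.
- **That the 0.10 type I error limit fails.** With the rule of 3 or more responses kept, a smaller cohort lowers the type I error.
- **That counting every treated patient removes the problem at no cost.** If 30% applies to evaluable patients and the inevaluable count as non-responders, the rate at 42% inevaluable is 0.30 × 7/12 = 17.5%, and the 0/7, 2/21 design then has about 62% power. It would also change the analysis population in Section 8.2.

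**Conclusion.** The concern holds in a conditional form. The allowance of 3 in 45 has no stated basis and conflicts with the response-evaluable count in Section 1.3.4. If both cohorts pass stage 1, neither 42 evaluable patients nor 90% power is assured.

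The patient count is fragile: the chance of reaching 42 is 33% at 10% inevaluable and 8% at 15%. Power is not. It is about 0.89 at 15%, close to the lower confidence limit for 5/12, and 0.86 at 30%. It reaches 0.78 only near 42%, where the chance of missing an active agent rises from about 10% to 22%. Type I error remains below 0.10.

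These figures assume a 30% response rate among evaluable patients, both cohorts continuing with an equal split, and the rule of 3 or more responses kept. The true inevaluable rate in the new cohorts cannot be learned from the documents.

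**What to change.** Amend the text of Section 8:

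1. Reconcile its 12 evaluable patients with the 7 evaluable for response in Section 1.3.4, and report the first group's response rate on the reconciled denominator.
2. Reconcile the length of a full course between Section 3.2 (three cycles) and Section 8.2 (4 cycles, 28 doses), because evaluability depends on it.
3. State the assumed inevaluable rate and its basis. Restate what the ceiling of 57 supports over a plausible range. For example, from 15% to 42% inevaluable, with both cohorts continuing, it gives about 38 to 26 evaluable patients and power of about 0.89 to 0.78 per cohort. Reaching 42 evaluable would take 50 to 72 new registrations, with the durations shown above.
4. State how a cohort that the ceiling ends below 21 evaluable will be declared, for example by keeping 3 or more responses and reporting the exact type I error and power at the size reached.

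The cost is wording, with stated power and duration slightly less favourable. No extra patients are required unless the sponsor chooses to raise the ceiling.

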## 8.1 METHODS OF ANALYSIS

Patients who are considered evaluable for response will be included in an analysis of time to progression. Time to progression will be estimated using the product-limit method of Kaplan and Meier. The probability of progression free survival at 6 months will be summarized. Response rates will be calculated as the percent of patients whose best response is a CR or PR, and the fraction of responses obtained will have a 95% confidence interval, which takes into consideration the two-stage nature of the design. Toxicity information recorded will include the type, severity, time of onset, time of resolution, and the probable association with the study regimen. Tables will be constructed to summarize the observed incidence by severity and type of toxicity.

**Time to progression** will be taken as the number of days from enrollment until: (1) disease progression; (2) death because of treatment complications; (3) resection of measurable tumor; or (4) last patient follow-up whichever is first. Patients will be considered to have experienced a progression event if (1) or (2) occurs. Otherwise, the patient will be considered censored for time to progression.

## 8.3 SECONDARY ENDPOINTS:

Pharmacokinetic analysis will be conducted using non-compartmental methods. For pharmacodynamic endpoints, descriptive statistics will be used for each endpoint. Briefly,

pharmacokinetics and molecular endpoints in target tissues will be assessed before and after mithramycin treatment, with the primary focus being comparison of microarray, qRT-PCR and IHC results relative to profiles identified in our preclinical studies. It is anticipated that non-parametric statistical methods will be used to compare paired results before and after treatment (but not between groups), as well as to perform comparisons or correlations among parameters. As the exact set of comparisons and analyses to be performed will be determined following completion of the trials, and will be based on limited numbers of patients, the analyses will be considered exploratory and hypothesis generating rather than definitive. The results of these descriptive analyses will be used to design further studies.

## **9 COLLABORATIVE AGREEMENTS**

### **9.1 AGREEMENT TYPE**

*N/A*

## **10 HUMAN SUBJECTS PROTECTIONS**

### **10.1 RATIONALE FOR SUBJECT SELECTION**

The patients to be entered on this protocol have advanced malignancies involving lungs, esophagus, or pleura and have limited life expectancies. This population was selected because of the unknown outcome of this treatment in terms of its effectiveness. The experimental treatment has a chance to provide clinical benefit although this is unknown. Subjects of both genders and all racial/ethnic groups are eligible. Efforts will be made to extend accrual to a representative population, but in this preliminary study, a balance must be struck between patient safety considerations and limitations on the number of individuals exposed to potentially toxic and/or ineffective treatments on the one hand and the need to explore gender and ethnic aspects of clinical research on the other hand. If differences in outcome that correlate with gender or ethnic identity are noted, accrual may be expanded, or a follow-up study may be written to investigate these differences more fully. One strategy for recruitment may be to distribute an IRB approved protocol recruitment letter to General and Oncology physicians and nurses.

